6.2.3 Follow-up Visits

As described in the Evaluations Table, dates for follow up measurements will be relative to baseline/enrollment. This is defined as the date of the enrollment phone call. Data will be extracted from the EHR and VDW as described above. There will be one follow up call/e-mail to administer the FCMAHS 3 months after enrollment for care partners who have opted to complete it.

6.2.4 Completion/Final Evaluation

As described above, there will be one follow up phone call/e-mail to administer the FCMAHS 3 months after enrollment. Care partners who do not wish to complete the FCMAHS by phone will be offered an electronic version and will be e-mailed a link. All

other data will be extracted from the EHR and VDW. If participants discontinue the intervention early (eg, by opting out during the pharmacist phone call), we will still extract their data from the EHR and VDW but will not offer the FCMAHS.

7 SAFETY ASSESSMENTS

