6.2.1 Screening Evaluation Consenting Procedure

As described in section 4.3, initial eligibility will be determined based on available clinical and claims data under a waiver of HIPAA Authorization.

Project assistants will serve as scheduling coordinators for the pilot study. Dyads who do not opt out (and those who opt in) will be called by the project assistant approximately 14 days after the study materials are mailed. Using the same approach that clinic staff use to call patients with dementia on the phone and identify their care partners during the course of clinical care, the project assistant will use an IRB-approved script (attached) to describe the pharmacist consult and assess interest. If the patient declines to identify a care partner and does not have a care partner listed in the EHR, the dyad will not be eligible. This phone call is described in section 4.3.

Participation in the pharmacist consult is not contingent on completion of the secondary outcome measure, FCMAHS. After scheduling the pharmacist consult, project assistants will offer care partners the option of completing the FCMAHS. They will obtain verbal consent for the FCMAHS when administering it over the phone (see script). If the care partner cannot complete the FCMAHS over the phone during the scheduling phone call,

the project assistant will offer to call back before the pharmacist visit (up to 28 days) or to later e-mail them a link to an electronic version.

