- Change in pMRCI from baseline to 3 months.

Chronic medication count will be obtained from the EHR using algorithms refined in OPTIMIZE.

In Aim 2b, feasibility will be measured as follows:

- Response rate and completion time for the FCMAHS using each mode of administration.
- Change in FCMAHS from baseline to 3 months.

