9.5 Data Analyses

In Aims 1 and 2a, our focus will be on descriptive statistics (counts and proportions). In Aim 2b, the primary analyses will rely on intention-to-treat analysis to present the comparative results of the trial. All events following randomization will be counted. Analyses using post-randomization data (eg, intervention compliance) will be discussed as secondary analyses. We will distinguish non-compliance with intervention from non-compliance with follow-up (ie, missing data).

For our primary outcome measure, pMRCI, we will first perform correlation analyses between chronic medication count and pMRCI scores at baseline. We will analyze changes in pMRCI before and after intervention and evaluate the impact of intervention assignment on the change scores using linear regression. The cluster by health system effect will be accounted for in the calculation of robust standard errors. Given the pilot nature of this trial, we will focus on estimates of precision in detecting treatment effects that will aid in the planning of a larger, sufficiently powered ePCT. We will also explore treatment effects by gender, age strata and race/ethnicity, again focusing on estimates of with-stratum variabilities instead of statistical significance. We will use multiple imputation to account for missing data.

For our secondary outcome measure, FCMAHS, we will first construct summary scores of the FCMAHS subscales using principal components analysis. We will then analyze changes in FCMAHS before and after intervention and evaluate the impact of intervention assignment on the change scores using linear regression.

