11.2 Informed Consent Forms

This pragmatic intervention adheres to standard clinical practice for older adults with dementia. The intervention is delivered by clinical pharmacists who are already integrated in primary care clinics at JHCP and KPCO and have considerable experience doing medication reviews with older adults, patients with dementia and care partners. The pharmacists are trained in complex geriatric medication management and routinely provide comprehensive medication management to Medicare beneficiaries. ALIGN provides structured templates for these existing comprehensive medication management phone calls, to focus them around dementia and to align medications with goals of care.

Options for pragmatic trial consent range from 1) full individual level recruitment and written informed consent, to 2) recruitment information sent to all eligible candidates with an 'opt out' clause, to 3) general information on the intervention provided to all eligible patients with an option for further inquiry. We request a waiver of informed consent (option 2) as an acceptable approach for the intervention, audio-recording of the pharmacist visit, and data collection from the EHR. This is based on the following factors:

(i) The research involves no more than minimal risk to the subjects.

- Any changes in medication regimens will be made by the pharmacist, PCP and patient/care partner through shared decision making. This is consistent with usual care.

- Comprehensive medication management is already part of the KPCO and JHCP standard of care.

- There is no requirement for patients/ care partners or PCPs to engage in discussions about medication optimization upon receipt of intervention materials.

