(iv) The waiver or alteration will not adversely affect the rights and welfare of the subjects: Intervention materials will include an informational cover letter that will indicate that dyads may wish to discuss medication discontinuation with the pharmacist but are under no obligation to do so. It will explain that because this is a new clinical program, appointments are limited and the pharmacist consult may be scheduled up to 3 months out. This is consistent with usual care, in which non-urgent appointments are typically made at least 3 months out.

(v) Whenever appropriate, the subjects or legally authorized representatives will be provided with additional pertinent information after participation.

We do not currently have plans to provide study subjects with information after the study ends. However, we could provide a summary of the study and its main findings to the individual clinics and they may distribute it through patient newsletters if they wish. We may also share the key findings with both health care systems and they may disseminate the information to their patients as they see fit.

For Aim 2b, we will obtain verbal informed consent to administer the Family Caregiver Medication Administration Hassles Scale (FCMAHS). After scheduling the pharmacist consult with interested care partners, project assistants will offer the FCMAHS. They will explain that **the pharmacist consult is not contingent on completion of the questionnaire**. If the care partner is interested in completing the FCMAHS, the project assistant will obtain verbal informed consent for either the telephone or web version, according to the care partner's preference (see attached script). The project assistant will offer to administer the FCMAHS as part of the same phone call or to call back before the pharmacist visit (up to 28 days later). They will tell care partners that they will call back to administer the FCMAHS once more about 3 months after enrollment, defined as the date of the scheduling phone call.

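### Section 6.2.4 withholds the 3-month FCMAHS from dyads who stop the intervention early, so a post-randomization event becomes missing Aim 2b data despite the intention-to-treat plan

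*Combined protocol and SAP*

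**What the plan says.** Section 6.2.4 describes one follow-up contact, by phone or e-mail, to administer the FCMAHS 3 months after enrollment. It then deals with participants who stop the intervention early, giving opting out during the pharmacist call as an example: "we will still extract their data from the EHR and VDW but will not offer the FCMAHS".

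The analysis sections take a different line. Section 9.5, like 9.1, states: "In Aim 2b, the primary analyses will rely on intention-to-treat analysis to present the comparative results of the trial". Both sections also state: "We will distinguish non-compliance with intervention from non-compliance with follow-up (ie, missing data". Section 9.4 lists among the Aim 2b measures "Change in FCMAHS from baseline to 3 months".

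Elsewhere the survey and the consult are handled separately. Section 6.2.1 says: "Participation in the pharmacist consult is not contingent on completion of the secondary outcome measure, FCMAHS". In Section 11.2 the FCMAHS has its own verbal consent, while the requested waiver is described as an "acceptable approach for the intervention, audio-recording of the pharmacist visit, and data collection from the EHR". Of the project assistants, the same section says: "They will tell care partners that they will call back to administer the FCMAHS once more about 3 months after enrollment".

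**The concern.** An intention-to-treat comparison needs the outcome from everyone randomized as far as it can be obtained, whether or not they stayed with the intervention. Sections 6.2.2 and 9.2.1 place randomization before the scheduling call, so a dyad that opts out during the pharmacist call is already in the trial. Section 6.2.4 nevertheless ends survey follow-up for that dyad, though passive record follow-up goes on.

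What is at stake is the FCMAHS change estimate passed to the ePCT. The pMRCI and the chronic medication count are unaffected, because EHR and VDW extraction continues. The pilot is also meant to develop the collection procedures for the full trial (Section 3). A rule that skips discontinuers could carry forward, and the pilot would not show whether they can be surveyed.

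**Working it through.** **1. Is the score lost by design?** Change to 3 months needs a 3-month score. Under 6.2.4 an early discontinuer is not offered the instrument, so no change score can exist for that care partner. Section 6.2.3 describes the 3-month contact for care partners who opted to complete the survey. It is best read as the general rule, with 6.2.4 as the exception.

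**2. Could the analysis repair it?** Multiple imputation is named in 9.1 and 9.5 only in the pMRCI paragraph. If it were applied to the FCMAHS, no discontinuer would have been asked at 3 months, so imputed values would borrow from those who stayed. The trial's data could not test that assumption. The pharmacist status reports (5.2) and the tracking log (6.2) can show who was not asked, but not what they would have scored.

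**3. Does it fall equally on the arms?**
- Survey window (6.1): Day 90 ± 45, that is Day 45 to 135.
- Immediate consult (6.2.2): within 4 weeks, about Day 28.
- Delayed consult (6.2.2): 3–4 months, about Day 90 to 120.

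Opting out during the pharmacist call would therefore be expected before the survey mainly in the immediate arm. This is not certain. The protocol's case is only an example, the second pharmacist call has no date (5.1), and delayed dyads can cancel before their consult.

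**4. The plan's own precision figure.** Section 9.2 gives 30 dyads per arm, 10% attrition, SD 1 and a 95% interval width of 0.4 SD. With 30 × 0.9 = 27, the half-width for one arm's mean is t(0.975, 26)/√27 = 0.396. The 0.4 reproduces only as a one-arm half-width. For the difference between arms the half-width is t(0.975, 52) × √(1/27 + 1/27) = 0.546. At 18 per arm (60% of 30) it is 0.677.

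**5. Size under assumed rates.** The documents give no survey-consent rate, discontinuation rate or difference in scores. Assumed ranges: consent c = 60–100%; share of consenting care partners who stop before the survey p = 10–20%; gap g between discontinuers and others = 0.5–1.0 SD.

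Not asked in an arm = 30 × c × p:

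| | p = 0.1 | p = 0.2 |
|---|---|---|
| c = 0.6 | 1.8 | 3.6 |
| c = 1.0 | 3.0 | 6.0 |

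Shift in that arm's mean change = p × g:

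| | g = 0.5 | g = 1.0 |
|---|---|---|
| p = 0.1 | 0.05 | 0.10 |
| p = 0.2 | 0.10 | 0.20 |

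Between-arm shift = (p − q) × g, where q is the share affected in the delayed arm and the gap is the same in both arms. With q = 0 it is 0.05–0.20 SD; with p = 0.2 and q = 0.1 it is 0.05–0.10 SD; with q = p it is 0.

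**6. What the remedy would recover.** Only those who answer are recovered. With response r1 = 0.8 in stayers and r2 = 0.5 in discontinuers (assumed), the part of the shift removed is g × p × r2 / ((1 − p) × r1 + p × r2):
- p = 0.1: 0.05/0.77 = 0.065 × g, that is 0.032 to 0.065 SD.
- p = 0.2: 0.10/0.74 = 0.135 × g, that is 0.068 to 0.135 SD.

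If r2 = r1, all of the shift is removed.

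**The case against.** The strongest defence is that the separation runs one way. The plan says the consult does not depend on the survey; it never says the survey is independent of the consult, and the survey is offered only once a consult has been scheduled. Under a consent waiver with opt-out, ending active contact after an opt-out while keeping passive record data is a defensible choice. That has some force, but 6.2.4 gives no such reason, and a care partner who separately agreed to the survey has not refused it by leaving the pharmacist call.

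Other points stand in part:
- The rule covers early discontinuation, not every form of non-compliance. A dyad that misses the second call is not clearly excluded.
- The records let the team label discontinuers and non-responders separately. What is lost is the score, not the label.
- The call-back described in 11.2 can be read as a general statement to which 6.2.4 is an exception, so that mismatch is secondary.
- The 10% attrition in 9.2 is undefined and may already include discontinuers; at full consent and p = 0.1, the 3 not asked equal that allowance. This bears on precision, not on selection.
- Dyads who decline on the scheduling call are also already randomized and never offered the survey. The remedy here does not close that separate gap.
- The effect sizes are all assumed, and Aim 2b is mainly about feasibility.

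**Conclusion.** The concern holds. As written, 6.2.4 turns early discontinuation into missing 3-month FCMAHS data, and the intention-to-treat comparison in 9.1 and 9.5 cannot be made on observed scores for those care partners. This follows from the text and needs no assumed rate.

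The size does rest on assumptions: roughly 2–6 care partners in an arm not asked, a one-arm shift of 0.05–0.20 SD, and a between-arm shift from 0 to 0.20 SD depending on how evenly the arms are affected. The direction is unknown, since discontinuers may have more hassles, or few and little to gain. An excess loss in the immediate arm is plausible and held with moderate confidence. The bias is smaller than the sampling error of the comparison (half-width 0.55 to 0.68 SD). No loss in response rate is claimed, because 9.4 sets no denominator for it. For a secondary outcome in a pilot without statistical hypotheses the harm is minor to moderate, but the correction is cheap and should be made.

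**What to change.** Replace the final clause of 6.2.4 with wording such as: *The 3-month FCMAHS will be offered to every care partner who consented to it, whether or not the pharmacist process was stopped, unless they decline the survey itself.*

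Report the 3-month response rate by arm with all consenting care partners as the denominator. List separately those who stopped the intervention (from the status reports in 5.2) and those who were asked but did not respond. State in 9.5 how missing FCMAHS scores will be handled. If the team prefers to keep the present rule, it should give the reason and amend the intention-to-treat wording for Aim 2b in 9.1 and 9.5.

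The cost is one sentence of protocol text, brief reporting and analysis wording, and a few extra survey offers, about 2–6 in an arm at the assumed rates. Some care partners who stopped may not welcome another contact; they can decline.

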7.1 Specification of Safety Parameters

Comprehensive medication management is already part of the KPCO and JHCP standard of care, and any changes in medication regimens will be made by the pharmacist, PCP and patient/care partner through shared decision making. This is consistent with usual care. There is no requirement for patients, care partners, or PCPs to engage in discussions about medication optimization upon receipt of intervention materials. The intervention is educational and designed to offer care partners the opportunity to discuss optimal medication use. The intervention does not in itself alter patient medication prescribing.

There is still the potential for adverse effects or unintended consequences from the intervention including: inadvertent stopping of necessary medications by patients or care partners and associated effects of those potential discontinuations, longer patient-PCP visit encounters devoted to medication discussions or clarifying misunderstandings, and lower satisfaction of patients/ care partners about medication management. If PCPs and patients or care partners elect to discontinue specific medications, there is the potential for recurrent symptoms, adverse drug withdrawal events, and anxiety about the deprescribing process. Potential risks can be minimized or prevented by using a patient-centered, pharmacist-led, structured deprescribing process, such as ALIGN. The intervention brochure and template for the pharmacist visit will include language that instructs the dyad not to stop any medications without talking to the pharmacist or PCP.

7.2 Methods and Timing for Assessing, Recording, and Analyzing Safety Parameters

Throughout the study period any physician, pharmacist or health care staff member will be able to report concerns about a safety issue that arises via a dedicated, monitored study email address and phone number as well as via contacting the PIs at each site ([name] at Johns Hopkins; [name] at KPCO). In addition, during the pilot study, study staff will review medical records of all patient participants who have ED visits, hospitalizations, or observation admissions to assess whether any emergency services were likely to have resulted from medication discontinuation. We will also assess whether emergency services were likely to have resulted from adverse effects of non-discontinued medications. Information on use of emergency services will inform the development of safety procedures for the future pragmatic trial.

7.3 Adverse Events and Serious Adverse Events

We define adverse events as any new negative diagnosis or symptom during the study period that results in seeking medical care. Serious adverse events will be those requiring the use of emergency hospital services. In the ADRD-MCC population we anticipate a baseline hospitalization rate of approximately 30% due to morbidity burden. As described above, we will review medical records of all patients who use emergency hospital services during the pilot study period and use this information to inform adverse event monitoring for the future pragmatic trial. Each month, project assistants will also review the list of enrolled patients who have received intervention materials for any uses of hospital emergency services. These cases will be targeted for record review by the site PI.

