- Potential risks of deprescribing can be minimized or prevented by using a patient-centered, pharmacist-led, structured process, such as ALIGN. Any medication believed to have increased potential for physiologic withdrawal, such as benzodiazepines, will undergo a prescribed drug taper under the clinical pharmacist's supervision according to standard clinical procedure. In addition, patients and care partners will be told that they can contact the pharmacist with any concerns about drug withdrawal effects or medical condition exacerbation. Further, medications can be restarted or increased at any time should concerns arise on the part of the patient, care partner or PCP. The intervention brochure and template for the pharmacist visit will include language that instructs the dyad not to stop any medications without talking to the pharmacist or PCP.

(ii) The research could not practicably be carried out without the requested waiver or alteration. Requiring full individual level recruitment and written informed consent would be highly burdensome to the target population, older adults with dementia, and would outweigh the minimal risks of the intervention itself. The standard procedures for assessing capacity, identifying a legally authorized representative and obtaining surrogate consent would likely cause many patients to opt out or become ineligible, which would compromise the scientific

29

validity of any evaluation of the intervention. Even if we consented care partners, the research cannot practicably be carried out without enrolling patients and care partners as dyads.

(iii) If the research involves using identifiable private information or identifiable biospecimens, the research could not practicably be carried out without using such information or biospecimens in an identifiable format:

The intervention is pragmatic and designed to test a scalable process that can be implemented across multiple clinics to improve care for PLWD. For this reason, our initial eligibility criteria and our primary outcome, the patient-level Medication Regimen Complexity Index, are derived from the EHR data under a waiver of HIPAA Authorization. The data need to be identifiable in order to recruit individual patients and care partners and to link subject data over time.

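### Section 7.3 counts only new diagnoses or symptoms as adverse events, so worsening of a known condition, a harm the protocol itself foresees, falls outside the definition

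*Combined protocol and SAP*

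**What the plan says.** Section 7.3 holds the only definition of an adverse event: "We define adverse events as any new negative diagnosis or symptom during the study period that results in seeking medical care". The next sentence reads: "Serious adverse events will be those requiring the use of emergency hospital services".

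Two other sections describe the harms that the intervention might cause. Section 7.1 says that if drugs are discontinued "there is the potential for recurrent symptoms, adverse drug withdrawal events, and anxiety about the deprescribing process". Section 11.2, in the argument for the consent waiver, says that "patients and care partners will be told that they can contact the pharmacist with any concerns about drug withdrawal effects or medical condition exacerbation". It also puts tapers of drugs with withdrawal potential under the pharmacist's supervision and notes that "medications can be restarted or increased at any time should concerns arise".

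Safety information is gathered in three ways:
- **Emergency use.** Study staff review the records of every patient with an ED visit, hospitalization or observation admission, "to assess whether any emergency services were likely to have resulted from medication discontinuation" (7.2). Project assistants also check monthly for use of hospital emergency services (7.3).
- **Open reporting.** Any physician, pharmacist or other health care staff member may raise a safety concern with the study (7.2).
- **Requested reporting.** Pharmacists and PCPs are asked to report events that they perceive as caused by the trial (7.3.1). Reported concerns go to the Safety Officer and the IRB (7.3.2).

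The schedule of evaluations (6.1) has no adverse-event row.

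**The concern.** In a deprescribing study, the harms of most interest are the return or worsening of whatever the drug was controlling, and withdrawal. A definition built on the word *new* suits a trial that adds a treatment. Here it fits least well for the events the intervention is most likely to cause, while an unrelated new illness qualifies without difficulty. The second condition, that care be sought, is undefined for the one contact that Section 11.2 specifically offers to dyads: a call to the clinical pharmacist.

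What is at stake is whether the pilot's event log can serve its purpose. Section 7.3 says that the review of emergency use will inform adverse-event monitoring in the later pragmatic trial. If the definition is carried forward as it stands, the larger trial inherits a category that leaves out foreseen harms. It also inherits a term that two sites, each with its own REDCap instance (10.2), could apply differently.

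**Working it through.** No arithmetic applies, because the plan states no figure that depends on the definition. The check is to take each harm that the protocol foresees and apply the two conditions in 7.3.

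| Harm foreseen | Where | Is it *new*? | Was care sought? |
|---|---|---|---|
| Exacerbation of a medical condition | 11.2 | No, if the condition is known and no new symptom appears | Depends on the contact made |
| Recurrent symptoms | 7.1 | Unclear: absent at baseline, but not new to the patient | Depends on the contact made |
| Withdrawal effects | 7.1, 11.2 | Usually yes, as a symptom first seen in the study period | Unclear if only the pharmacist is called |

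**Step 1: worsening.** Both conditions must be met. Worsening of a known condition fails the first, whatever care is sought. No other section extends the definition to worsening or recurrence.

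**Step 2: serious events.** The sentence on serious events follows directly from the one on adverse events and picks out those that need emergency hospital services. On that reading they are a subset, so an event that is not an adverse event cannot be a serious one. An emergency admission for worsening of a known condition would then be reviewed but not classified as serious. Section 7.3 anticipates a baseline hospitalization rate of approximately 30%, with no period given, so classifying admissions will be a practical task. The documents do not say what share would be worsening of a known condition.

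**Step 3: pharmacist contact.** Section 11.2 tells dyads that they can call the pharmacist about withdrawal or exacerbation. Nothing says whether that call counts as seeking care. If it does, a new withdrawal symptom qualifies. If it does not, the same symptom settled by telephone need not be counted.

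**Step 4: what the other routes catch.** The emergency review does not use the word *new*, so it finds worsening that leads to the hospital. It asks about discontinued drugs and about adverse effects of drugs that were not discontinued; dose reduction is not named as a cause to assess. Below the emergency level nothing is systematically solicited, and capture depends on someone choosing to report.

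**The case against.** The strongest case on the other side is that safety capture here does not rest mainly on the definition. Emergency use is reviewed for every patient whatever the diagnosis. Open reporting under 7.2 has neither a newness nor a care-seeking condition. The pharmacist who takes a withdrawal call is one of the people whom 7.3.1 asks to report. This stands, and it confines the gap to classification and to non-emergency events.

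It is also fair that a withdrawal symptom is ordinarily new, and that calling a pharmacist embedded in the primary care clinic can reasonably be read as seeking care. Those events are therefore ambiguous, not excluded. Only worsening of a known condition clearly falls outside.

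Three stronger readings are tempting, and the documents do not support them:
- A reader might infer that the pilot's observed harm will be biased downward. No adverse-event rate or between-arm safety comparison is planned (9.1, 9.5), and the emergency review, which is what feeds into the later trial, is not limited by the word *new*.
- A reader might infer that the minimal-risk argument for the waiver fails. In 11.2 that argument rests on shared decisions, usual care and supervised tapers, not on an event count from this pilot.
- A reader might infer that a stop later reversed is scored as a success. Acceptance measures agreement by the dyad and the PCP (9.4), not sustained stopping. A restarted drug that meets the chronic-medication definition at 3 months is back in the medication count, and a drug on the regimen then contributes to the pMRCI, although neither measure identifies the restart as such.

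**Conclusion.** The point holds as an inconsistency between Section 7.3 and Sections 7.1 and 11.2. Worsening of a known condition after a drug change is a foreseen harm that the definition, read literally, leaves out of both adverse and serious adverse events. Recurrence and pharmacist-managed withdrawal are left to the reader's interpretation.

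The size cannot be estimated. The documents give no frequency for recurrence, exacerbation or withdrawal, and no expected number of patients with a drug change, so any count would rest on invented inputs. The conclusion assumes that *new* is read in its ordinary sense and that serious events are a subset of adverse events. If the sites in practice record worsening as an adverse event, the fault is one of wording only and the correction still applies.

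**What to change.** Reconcile 7.1, 7.3 and 11.2:
- In 7.3, widen the definition to *any new, recurrent or worsening diagnosis or symptom*, keeping the rest of the sentence. Serious events then follow without further change.
- In 7.3, state whether contact with the clinical pharmacist counts as seeking medical care, so that both sites classify such calls alike.
- If it counts, report pharmacist-detected events separately from the others. The immediate arm is scheduled for its pharmacist visit within 4 weeks and the delayed arm only 3 to 4 months after enrollment (6.2.2), so the immediate arm has more opportunity to have such events noticed in the first 3 months.
- Optionally, describe from the EHR any restart or increase of a drug that had been changed, beside the acceptance rate. This needs drug-level tracking and a stated time window, so it is more than one extra field.

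The required part costs a few sentences in 7.3. The downsides are more minor events to log and, for pharmacist-detected events, unequal ascertainment between arms, which separate reporting makes visible but does not remove. The change affects what is recorded, not how patients are managed.
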